4. STUDY DESIGN

4.1 Overview of Study Design

This is an open-label single arm Phase II study in subjects with AML or high-risk MDS in CR/CRi. Patients will receive single 4mg oral dose of ixazomib on days 1, 8 and 15 of each 28-day cycle. Treatment with ixazomib will be administered for 12 cycles for patients who remain in CR.

For patients with MRD positive CR/CRi at study start, treatment with ixazomib may continue for a total of 12 cycles after achievement of MRD negativity is observed.

Patients who are experiencing clinical benefit may be eligible to continue therapy after the allotted 12 cycles after discussion with the PI and the discussion documented in the patient's medical record.

Subjects will be assessed for outcome status (i.e. maintenance of CR/CRi) every 3 cycles or as clinically indicated. Adverse events, compliance and concomitant medications will be assessed continually throughout the study; specific information will be requested at each study visit.

Study cycles will be administered every 28 days ± 5 days or upon resolution of any clinically significant study drug related AE to grade 0-1, whichever occurs first.

Administration of subsequent cycles should be administered when neutrophils recover to \geq

0.5 x 10⁹/L and platelets to \geq 50 x 10⁹/L, or to baseline levels prior to the start of the last cycle of therapy.

Ixazomib will be self-administered primarily on an outpatient basis; but may be administered as an inpatient. Patient compliance will be documented using the MD Anderson (MDACC) Research Medication Diary and will be assessed at each study visit.

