6.2 Study Drug Administration

Study calendar

PROCEDURES	Pre-Study Screen ^o	Cycle 1 Day 1	Cycle 1 Day 8	Cycle 1 Day 15	Day 1 of Cycle 2 onwards (+/- 5 days)	End of Treatment (+/- 5 days)
Informed Consent	Х					
Medical History	Х					
Vital Signs (including	Х	Х	Х	Х	Х	Х
temperature, pulse and blood						
pressure)						
Confidential		2	7		V8 1	1May15

Version 8 - 2014-0379

Physical Exam and	Х	Х			Х	Х
Performance Status						
Concomitant Medications	Х	х			Х	Х
CBC with differential	X*	х	X²	X ²	X ¹ , ²	Х
Blood Chemistries	X*	Х	Х	Х	Х	Х
Bone marrow aspiration and/or biopsy	X				X³	Х
IPSS score &/or WHO disease classification	X					
Pregnancy Test (females of child-bearing potential only)	Xţ					
AE and SAE assessment	Х	Х	Х	Х	Х	Х

°Screening must be performed within 4 weeks prior to study drug initiation / study start unless otherwise indicated *CBC with differential and blood chemistries (sodium, potassium, BUN, creatinine, glucose, AST and/or ALT, total bilirubin, alkaline phosphate) must be performed within 72 hours of Cycle 1 Day 1

†Within 7 days of Day 1 in females of child-bearing potential

¹ANC must be \geq 500/mm³ and platelet count must be \geq 50,000/mm³, or have recovered to baseline hematologic values ²If platelet count \leq 25,000/mm³ or ANC \leq 500/mm³ on any ixazomib dosing day, CBC should be repeated twice weekly until counts have exceeded the prespecified values (as per Section 6.3.1)

³Bone marrow aspiration and/or biopsy required for study entry, and every 3 cycles for primary outcome unless required more frequently as clinically indicated.

Ixazomib will be self-administered primarily on an outpatient basis; but may be administered as an inpatient. 3 doses of ixazomib corresponding to the three treatment days (days 1, 8 and 15) will be dispensed for the first cycle. For subsequent cycles, up to 1 month of therapy (3 doses) may be dispensed.

On day 1 (+/- 5 days) of each cycle the following procedures will be performed and

documented: physical exam including vital signs and performance status, evaluation of concomitant medications, laboratory analysis including CBC and serum chemistries, and assessment of any side effects.

Subjects will be assessed for outcome status (i.e. maintenance of CR/CRi) every 3 cycles or as clinically indicated. Adverse events, compliance and concomitant medications will be assessed continually throughout the study; specific information will be requested at each study visit.

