Patient compliance will be documented using the MD Anderson (MDACC) Research Medication Diary and will be assessed at each study visit.

Destruction of unused study drug will be in accordance with the institution's drug destruction policy.

Ixazomib Administration

All protocol-specific criteria for administration of study drug must be met and documented before drug administration. Study drug will be administered or dispensed only to eligible patients under the supervision of the investigator or identified subinvestigator(s). Patients should be monitored for toxicity, as necessary, and doses of ixazomib should be modified as needed to accommodate patient tolerance to treatment; this may include symptomatic treatment, dose interruptions, and adjustments of ixazomib dose (see Section 6.3).

Capsules of ixazomib will also be referred to as study drug. Study drug will be supplied by Millennium as capsules of 2.3, 3.0 and 4.0 mg ixazomib.

The prescribed administration of ixazomib doses in this study is 4mg ixazomib on days 1, 8 and 15 in a 28 day cycle.

Patients should be instructed to swallow ixazomib capsules whole, with water, and not to break, chew, or open the capsules. Study drug should be taken on an empty stomach (no food or drink) at least 1 hour before or 2 hours after a meal. Each capsule should be swallowed separately with a sip of water. A total of approximately 8 ounces (240 mL) of water should be taken with the capsules.

Missed doses can be taken as soon as the patient remembers if the next scheduled dose is 72 hours or more away. A double dose should not be taken to make up for a missed dose. If the patient vomits after taking a dose, the patient should not repeat the dose but should resume dosing at the time of the next scheduled dose.

Ixazomib Destruction

Investigational ixazomib (expired or end of study) should be destroyed on site according to the institution's standard operating procedure. Be sure to document removal and destruction on drug accountability logs.

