6.3 Dose-Modification Guidelines

6.3.1 Recommended ixazomib Criteria for Beginning or Delaying a Subsequent Treatment Cycle & Dose Modifications for Treatment Associated Toxicity

Treatment with ixazomib will use a cycle length of 28 days. For a new cycle of treatment to begin, the patient must meet the following criteria:

- ANC must be ≥ 500/mm³ and platelet count must be ≥ 50,000/mm³, or have recovered to baseline hematologic values
- All other nonhematologic toxicity (except for alopecia) must have resolved to ≤ Grade 1 or to the patient's baseline condition

If the patient fails to meet the above-cited criteria for initiation of the next cycle of treatment, dosing should be delayed for 1 week. At the end of that time, the patient should be re-evaluated to determine whether the criteria have been met. If the patient continues to fail to meet the above-cited criteria, delay therapy and continue to re evaluate. The maximum delay before treatment should be discontinued will be 4 weeks or at the discretion of the Principal Investigator.

All decisions for dose adjustments will be made by the MD Anderson treating physician.

For dosing recommendations upon recovery, refer to Table 6-2 and Table 6-3. Dose adjustments different than those described below are acceptable after discussion with the PI, and will require documentation of the rationale for such action.

Table 6-1 MLN908 Dose Adjustments

Dose (mg)
4.0 mg
3.0 mg
2.3 mg
Discontinue

Dosage adjustments for hematologic toxicity are outlined in Table 6-2.

Criteria	Action	
Within-Cycle Dose Modifications		
 If platelet count ≤ 25 × 10⁹/L or ANC ≤ 0.50 × 10⁹/L on a ixazomib dosing day (other than Day 1) 	 ixazomib dose should be withheld. Complete blood count (CBC) with differential should be repeated twice weekly until the ANC and/or platelet counts have exceeded the prespecified values (see Section 6.3.1) on at least 2 occasions. Upon recovery, ixazomib may be reinitiated with 1 dose level reduction. 	
Dose Modifications for Subsequent Treatment Cycles		

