 Delay of > 2 weeks in the start of a subsequent cycle due to lack of toxicity recovery as defined in Section 6.2ANC < 0.50 × 10⁹/L, platelet count < 50 × 10⁹/L, or other nonhematologic toxicities > Grade 1 or not to the patient's baseline condition 	 Hold ixazomib until resolution as per criteria Section 6.3. Upon recovery, reduce ixazomib 1 dose level. The maximum delay before treatment should discontinued will be 4 weeks or at the discretion of the PI. 	
Dose Modifications for Subsequent Treatment Cycles		
All hematologic toxicities	 For hematologic toxicity that occurs during a cycle but recovers in time for the start of the next cycle,: If dose was reduced within the cycle, start the next cycle at that same dose. If due to toxicity timing, ie, after Day 15 dosing thus a dose reduction was not required at that point in the cycle, reduce ixazomil by 1 dose level at the start of that cycle. Do not reduce the dose both within a cycle and at the start of the cycle for the same most severe toxicity. 	

Table 6-2ixazomib Dose Adjustments for Treatment Related Hematologic
Toxicities

Treatment modifications due to ixazomib -related AEs are outlined in Table 6-3.

Table 6-3Ixazomib Treatment Modification (Delays, Reductions, and
Discontinuations) Due to Treatment Related Adverse Events (Non-
Hematologic Toxicities)

Adverse Event (Severity)	Action on Study Drug	Further Considerations
Peripheral Neuropathy: Grade 1	• No action	Grade 1 signs and symptoms: asymptomatic; without pain or loss of function; clinical or diagnostic observations only [14]
New or worsening Grade 1 peripheral neuropathy with pain or Grade 2	 May hold study drug until resolution to Grade ≤ 1 or baseline 	Grade 2 signs and symptoms: Moderate symptoms; limiting instrumental activities of daily living (ADL) [14]
New or worsening Grade 2 peripheral neuropathy with pain or Grade 3	 Hold study drug until resolution to Grade ≤ 1 or baseline Reduce study drug to next lower dose upon recovery 	Grade 3 signs and symptoms: severe symptoms; limiting self- care ADL; assistive device indicated [14]
New or worsening Grade 4 peripheral neuropathy	Discontinue study drug	
Grade 2 Rash	• Symptomatic recommendations as per section 6.7	The investigator and project clinician may discuss considerations for dose modifications and symptom management.

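### Section 4.1 lets a new cycle start on schedule over an unresolved drug-related non-hematologic AE, which Section 6.3.1 forbids

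*Combined protocol and SAP*

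**What the plan says.** **Section 4.1 (Overview of Study Design)** gives cycles every 28 ± 5 days "or upon resolution of any clinically significant study drug related AE to grade 0-1, whichever occurs first". The next sentence adds a blood-count condition: "Administration of subsequent cycles should be administered when neutrophils recover to" at least 0.5 × 10⁹/L and platelets to at least 50 × 10⁹/L, or to the levels before the last cycle. Section 4.1 sets no further start condition and does not refer to Section 6.3.1.

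**Section 6.2, study calendar, footnote 1** also covers counts only: the same thresholds, "or have recovered to baseline hematologic values".

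**Section 6.3.1** makes its criteria for a new cycle mandatory. Besides the counts, it requires: "All other nonhematologic toxicity (except for alopecia) must have resolved to ≤ Grade 1" or to the patient's baseline. It continues: "If the patient fails to meet the above-cited criteria for initiation of the next cycle of treatment, dosing should be delayed for 1 week". Then: "At the end of that time, the patient should be re-evaluated to determine whether the criteria have been met". Further delay and re-evaluation follow if needed, up to 4 weeks or at the principal investigator's discretion.

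**Section 6.2 (Ixazomib Administration)** adds a general rule: "All protocol-specific criteria for administration of study drug must be met and documented before drug administration".

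**Table 6-3** holds drug for related Grade 3 non-hematologic toxicity and for Grade 3 or painful Grade 2 neuropathy. For Grade 2 neuropathy without pain the hold is optional ("May hold study drug until resolution to Grade" 1 or less, or baseline). For Grade 2 rash it lists only symptomatic measures.

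**The concern.** Two sections give different rules for the same decision. Under Section 4.1, resolution of an AE can only bring the start forward; it can never hold it back. Section 6.3.1 makes resolution a precondition. Because the sentence after the quoted one states the count gate, Section 4.1 reads like a complete start rule, and a clinician working from it could begin a cycle that Section 6.3.1 would delay.

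What is at stake is patient safety in dosing. From Cycle 2 onwards, Day 1 is the only scheduled on-treatment visit in the calendar, and up to three doses may be dispensed then, mainly for self-administration at home. A wrong decision on Day 1 can therefore release a whole cycle of drug. In addition, Table 6-2 calls for a one-level dose reduction when a cycle start slips by more than 2 weeks for lack of recovery. If Section 4.1 is followed, no delay builds up and that reduction is not triggered.

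**Working it through.** The plan states no figure on this point. The check is to write each rule as a start date and compare them.

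**Inputs.** Cycle length 28 days and window ± 5 days (Section 4.1); a 1-week delay followed by re-evaluation (Section 6.3.1). Counting the first day of the current cycle as Day 1, the next cycle is due on Day 1 + 28 = Day 29, with a window of Day 24 to Day 34. Let *r* be the day on which the AE reaches Grade 1 or less, and assume that counts are adequate.

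**Assumptions.** The values of *r* below are illustrative; the documents do not say how often AEs are unresolved when a cycle is due. The AE is assumed still present at a check on Day 29. Re-evaluation after the first week is assumed weekly; Section 6.3.1 says only that it continues.

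**Rules.**
- Section 4.1 as written: start = min(29, *r*).
- Section 4.1 with *first* changed to *later* and nothing else: start = max(29, *r*).
- Section 6.3.1: start = 29 if *r* ≤ 29; otherwise 29 + 7 × (number of weeks from Day 29 to *r*, rounded up).

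| *r* | 4.1 as written | Days before resolution, start on Day 29 | Same, across Day 34 to Day 24 | *Later* alone | 6.3.1 |
|---|---|---|---|---|---|
| 31 | 29 | 31 − 29 = 2 | – | 31 | 29 + 7 = 36 |
| 36 | 29 | 36 − 29 = 7 | 36 − 34 = 2 to 36 − 24 = 12 | 36 | 29 + 7 = 36 |
| 43 | 29 | 43 − 29 = 14 | 43 − 34 = 9 to 43 − 24 = 19 | 43 | 29 + 14 = 43 |

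**Reading the table.** In every row Section 4.1 permits a start on Day 29 with the AE still present, and Section 6.3.1 does not. The first row also shows that changing *first* to *later* is not enough: Day 31 is 36 − 31 = 5 days short of Section 6.3.1 once a Day 29 check has failed.

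**Which events are affected.**
- Low counts: not affected, because Section 4.1 has its own count gate, in line with Section 6.3.1.
- Related Grade 3 non-hematologic toxicity, and Grade 3 or painful Grade 2 neuropathy: Table 6-3 holds drug whatever Section 4.1 says.
- Related Grade 4: Table 6-3 says to discontinue for neuropathy and to consider permanent discontinuation otherwise.
- Grade 2 rash and Grade 2 neuropathy without pain: Table 6-3 does not require a hold. Section 6.3.1 is the mandatory gate, and Section 4.1 contradicts it.

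**The case against.** The strongest reply is that the operative text is already right. Section 4.1 is an overview, while Sections 6.2 and 6.3 govern dosing. Section 6.2 requires every administration criterion to be met and documented, and Section 6.3.1 is mandatory. The quoted sentence might be read as saying only when a cycle falls due, with the start criteria applied on top. Table 6-2 points the same way: its row for delayed starts names non-hematologic toxicity above Grade 1 and says to hold drug.

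Much of this stands as mitigation. Sections 6.2 and 6.3 should control in practice, and the reach is correspondingly small. But none of it corrects Section 4.1. The document as supplied has no clause saying which section prevails, and the heading of Section 6.3.1 calls its criteria recommended, which leaves some room to treat them as softer. The Table 6-2 row applies only after a delay of more than 2 weeks, so it confirms the intent of Section 6.3.1 without gating every start. The investigator's discretion in Section 6.3.1 concerns the maximum delay and dose adjustments, not waiving the start criteria.

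Three smaller points are fair. Calendar footnote 1 belongs to the blood-count row, so its silence on other toxicity proves little. The resolution days are chosen, not observed. And the 5-day shortfall depends on a formal failed check on Day 29: a first check on Day 31, inside the window, would pass Section 6.3.1 without delay.

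**Conclusion.** The concern holds. As written, Section 4.1 makes the cycle start the earlier of schedule and AE resolution, which permits what Section 6.3.1 forbids. The likely intent was the later of the two. The practical reach is mainly persistent drug-related Grade 2 non-hematologic AEs, for which Table 6-3 gives no mandatory hold.

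The size is illustrative: for AEs resolving on Day 36 or Day 43, Section 4.1 allows dosing 7 or 14 days before resolution (2 to 12 and 9 to 19 days across the window). This rests on the assumed resolution days, and the comparison with Section 6.3.1 on Day 43 also rests on weekly re-evaluation. No frequency can be given. The issue is a safety instruction that is wrong in one place and right in others; no consequence for relapse-free survival, the futility or toxicity rules, or any analysis is claimed.

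**What to change.** Replace the sentence in Section 4.1 so that it says the following, in whatever house wording is preferred: cycles are given every 28 ± 5 days, or once any clinically significant drug-related AE has returned to grade 0–1 or baseline, whichever is *later*; a new cycle starts only when all criteria in Section 6.3.1 are met, and delays are handled as in that section.

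The reference to Section 6.3.1 is essential. It brings in the 1-week delay and re-evaluation, and it covers all non-hematologic toxicity except alopecia, which is broader than the drug-related AEs named in Section 4.1. Deleting the AE clause and simply pointing to Section 6.3.1 would also remove the conflict.

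The cost is one replaced sentence, by protocol amendment. Tables 6-2 and 6-3, sample size, endpoints, visits and monitoring rules stay as they are.

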4.2 Number of Patients

This study is planned for 40 patients. All patients who receive at least one dose of the study drug will be included in the efficacy and safety analysis. Subjects who do not receive any dose of the study drug will be replaced.

4.3 Duration of Study

Treatment will continue until discontinuation due to relapse or disease progression, unacceptable toxicity, or completion of therapy. Completion of therapy includes 12 cycles of ixazomib. Note that in patients with MRD positive disease at study start, treatment may continue for 12 cycles after achievement of MRD negativity is observed. For patients experiencing clinical benefit, treatment may be continued beyond 12 cycles if in the best interest of the patient.

5. STUDY POPULATION

5.1 Inclusion Criteria

Each patient must meet all of the following inclusion criteria to be enrolled in the study:

- 1. Male or female patients 18 years of age or older.
- 2. Voluntary written consent must be given before performance of any study related procedure not part of standard medical care, with the understanding that consent may be withdrawn by the patient at any time without prejudice to future medical care.
- 3. Female patients who:

Confidential

- Are postmenopausal for at least 1 year before the screening visit, OR
- Are surgically sterile, OR
- If they are of childbearing potential, agree to practice 2 effective methods of contraception, at the same time, from the time of signing the informed consent form through 90 days after the last dose of study drug, OR
- Agree to practice true abstinence when this is in line with the preferred and usual lifestyle of the subject. (Periodic abstinence [eg, calendar, ovulation, symptothermal, post-ovulation methods] and withdrawal are not acceptable methods of contraception.)

Male patients, even if surgically sterilized (ie, status post-vasectomy), must agree to one of the following:

- Agree to practice effective barrier contraception during the entire study treatment period and through 90 days after the last dose of study drug, OR
- Agree to practice true abstinence when this is in line with the preferred and usual lifestyle of the subject. (Periodic abstinence (eg, calendar, ovulation, symptothermal, post-ovulation methods] and withdrawal are not acceptable methods of contraception.)
- Patients must have a history of *de novo* or therapy-related AML (defined by WHO classification of ≥20% bone marrow blasts) or high-risk MDS (defined by IPSS or IPSS-R)
- Patients must be in a documented CR/CRi from either their front-line or first salvage therapy as evidenced by <5% bone marrow blasts and absence of extramedullary disease. (For patients with prior MDS who then transformed to AML, therapy received for MDS is not considered prior therapy for AML)
- 6. Patients should have received at least 2 cycles of induction therapy or 1 induction and 1 consolidation cycle, OR patient should be considered to have completed all planned chemotherapy, OR patient is considered to be unable, unfit or unwilling to receive additional chemotherapy.
- 7. Eastern Cooperative Oncology Group (ECOG) performance 0, 1, or 2.
- 8. Patients must meet the following clinical laboratory criteria:

- Absolute neutrophil count (ANC) ≥ 500/mm³ and platelet count ≥ 50,000/mm³.
 Platelet transfusions to help patients meet eligibility criteria are not allowed within 3 days before study enrollment.
- Total bilirubin $\leq 1.5 \times$ the upper limit of the normal range (ULN).
- Alanine aminotransferase (ALT) and/or aspartate aminotransferase (AST) ≤ 3 × ULN.
- Calculated creatinine clearance \geq 30 mL/min

5.2 Exclusion Criteria

Patients meeting any of the following exclusion criteria are not to be enrolled in the study:

- 1. Female patients who are lactating or have a positive serum or urine pregnancy test during the screening period.
- Failure to have fully recovered (ie, ≤ Grade 1 toxicity) from the reversible effects of prior chemotherapy.
- 3. Major surgery within 14 days before enrollment.
- 4. Radiotherapy within 14 days before enrollment. If the involved field is small, 7 days will be considered a sufficient interval between treatment and administration of the ixazomib.
- 5. Known central nervous system involvement.
- 6. Infection requiring systemic antibiotic therapy or other serious infection within 14 days before study enrollment.
- 7. Evidence of current uncontrolled cardiovascular conditions, including sustained hypertension (SBP >150mmHg on two or more readings one week apart without normalization in between), clinically significant uncontrolled cardiac arrhythmias, Class III-IV NYHA congestive heart failure, or unstable angina, or myocardial infarction within the past 6 months.
- 8. Systemic treatment within 7 days, or the half life of the treatment, whichever is longer, before the first dose of ixazomib, with strong inhibitors of CYP1A2

(fluvoxamine, enoxacin, ciprofloxacin), strong inhibitors of CYP3A (clarithromycin, telithromycin, itraconazole, voriconazole, ketoconazole, nefazodone, posaconazole) or strong CYP3A inducers (rifampin, rifapentine, rifabutin, carbamazepine, phenytoin, phenobarbital), or use of Ginkgo biloba or St. John's wort.

- 9. Ongoing or active systemic infection, history of hepatitis B or C virus infection, or known human immunodeficiency virus (HIV) positive.
- 10. Any serious medical or psychiatric illness that could, in the investigator's opinion, potentially interfere with the completion of treatment according to this protocol.
- 11. Known allergy to any of the study medications, their analogues, or excipients in the various formulations of any agent.
- 12. Known GI disease or GI procedure that is expected to interfere with the oral absorption or tolerance of ixazomib including difficulty swallowing. As determined by investigator.
- 13. Diagnosed or treated for another malignancy within 2 years before study enrollment or previously diagnosed with another malignancy and have any evidence of residual disease. Patients with nonmelanoma skin cancer or carcinoma in situ of any type are not excluded if they have undergone complete resection.
- 14. Patient has ≥ Grade 3 peripheral neuropathy, or Grade 2 with pain on clinical examination during the screening period.
- 15. Administration of other investigational agents for the treatment of AML/MDS within 21days (or 5 times the terminal half life of the investigational treatment whichever is longer) of the start of this trial and throughout the duration of this trial.
- 16. At the time of registration, stem cell transplantation is not planned within the next 3 months.

